active-listening, and role plays, using BFT approaches. Lastly, it will use tips from Motivational Interviewing for eliciting SP encouragement for PE participation, creating a tailored plan for SPs to support PE, and assisting SPs in follow-up telephone calls. The training team is highly seasoned in educating providers in these methods. The training will be video-taped for use in training future providers (e.g., due to provider attrition during the course of the study).

5.1C. Standard PE.

Providers will deliver PE consistent with the standard of care, with a flexible end date as they typically would in routine practice and will divide Session 2 into 2a and 2b. VA PE trainings encourage extending the therapy as needed, routinely resulting in a range of 8 to 15 sessions. Posttreatment assessments will be scheduled to coincide with when Veterans complete treatment to allow for this flexible end date. If participants are still in treatment at 16 weeks post-session 1, the posttreatment assessment will be delayed to allow them to get through as much of the treatment as possible prior to assessment. If the Veteran never attends session 1, their posttreatment will be scheduled 16 post-first missed appointment for session 1.

Family attendance will not be solicited by providers in standard PE. If a SP contacts a provider, the provider will proceed as he/she would in his/her routine practice, consistent with our design emphasis on real-world care. Quantity and quality of provider-SP contact will be measured by weekly provider report. We anticipate risk for cross-over effects from SPs reaching out to providers is minimal as considerable effort is required by SPs to gain access to Veterans' providers (i.e., Veterans must request and sign a Release of Information). Additionally, while we did not capture who initiated the provider-SP contacts reported among 17% of SPs within Project HomeFront, qualitative interviews suggest these contacts are typically initiated by providers. In qualitative interviews, SPs were enthusiastic about being involved in Veterans' care, but few SPs had considered reaching out to Veterans' providers.

Table 2. Content Added for Family Supported PE	
PE#	Task
1	
 • Eliciting benefits of further SP attendance • Brief discussion of how SPs can help in PE
2a	
 • Brainstorm how SPs encourage/discourage PE adherence and approaching trauma-reminders

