2b	
 • Develop SP's plan for supporting adherence • Anticipate barriers to success; role play solutions
3, 5	
 • SP telephone check-ins for trouble-shooting support plan with longer in-person check-ins when indicated

5.1D. Family Supported PE (Table 2).

Providers will deliver the 10 session PE protocol as they typically would with additional material outlined session by session below. As discussed above, they will divide session 2 into 2a and 2b (11 total sessions delivered over an 11-16 week period). If the dyad is randomized to include their family in treatment sessions, SPs will attend the first session with the Veteran and be encouraged to attend both

session 2a and 2b (see Table 2). Each session attended by a family member will include the following content. We will ask Veterans in self-reports prior to session 1 about their preference for having their SP present for their Session 1 trauma discussion with their providers (i.e., trauma interview). This preference will be honored to promote early retention and keep the intervention Veteran-centered.

Session 1: The last twenty minutes of Session 1 will involve a) eliciting how further SP attendance could be of benefit the dyad, using Motivational Interviewing tips, b) discussion of how the SP can support PE participation should this be the only family session, c) and discussion of the benefits of talking further about trauma with loved ones, using Motivational Interviewing strategies.

Session 2a: We will devote fifteen minutes to discussing how SPs naturally encourage or discourage Veterans to approach trauma reminders and participate in treatment. Session 2b: Thirty minutes will be devoted to a) create a tailored plan for SPs to support Veterans' PE participation, including planning trauma disclosure to family when indicated or desired and b) problem-solving barriers to the success of the SPs' support plan.

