Our study sites have robust telemedicine programs that provide PE by telemedicine. Study sites will follow all procedures and regulations that are currently in place at their VA hospital and surrounding CBOCs to ensure services provided to Veterans are safe and accurate. Additionally, all practitioners treating patients using telemedicine will be qualified to deliver the level of consultation, care, and treatment involved.

5.1F. Defining Drop Outs

Participants could, without notice, stop coming to treatment, and then contact their providers several months later to request to re-initiate treatment. This could lead to vastly different periods of time that some participants are in treatment (watering down treatment effects and potentially artificially influencing study findings) and could also pose administrative problems if they would be unable to complete posttreatment or follow-up assessment during the period of funding for the project. Additionally, at some point such a break in treatment would become long enough such that starting treatment again would be equivalent to starting treatment over (e.g., like a new course of care). Consequently, any unanticipated break in treatment for longer than 6 consecutive weeks will trigger an official 'end' to their treatment period. Participants will remain in the study protocol (i.e., receive all study assessments and not removed from the study). They will be assessed at 16 weeks post session 1 for their posttreatment survey and interview. If they request to re-enter care, they will be referred to the clinic to intiate a new course of care with the clinic, outside of the study.

5.1G. Provider Monitoring and Fidelity Assessment.

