Veterans will be considered 'actively engaged in psychotherapy in our study' when their study therapist has not officially closed their therapy case. Cases are closed when the veteran has completed their course of PE, when the veteran tells their therapist they have quit PE, or when providers have exhausted outreach attempts to a veteran who has missed a scheduled session(s). SPs in the PE2 condition are considered 'actively engaged in psychotherapy in our study' when their veteran is actively engaged in psychotherapy in our study. SPs in the Standard PE condition are never considered 'actively engaged in psychotherapy in our study.'

Managing risk from CBOCs and in-home video telehealth sessions. Due to the nature and distance between the Veteran and telemental health provider incurred in telemedicine practice, additional measures will be taken to ensure patient safety. These procedures will be in place during all telemedicine sessions:

- a. Study providers will follow the guidelines detailed in the 2017 Department of Veteran Affairs National Telemental Health Supplement and the 2012 Telemental Health Suicide Prevention and Emergency Care manual.
- b. Providers will use VA approved electronic communication methods
- c. All study providers will follow their site's local telemental health policies and emergency procedures at each facility and clinic.
- d. Providers will always adhere to established face-to-face assessment protocols.
- e. Telemental health provider will have detailed contact information from the patient with particular attention to who could be contacted in the event of an emergency. All emergency contact information, local police phone numbers and local emergency room contact information should be readily retrievable during all sessions.
- f. Providers will use the National Telehealth Help Desk when necessary: [name].

Additional manners to manage risk from CBOCs.

- a. For all telemental health sessions at CBOC locations, a CBOC staff person will be available to assist Veteran should the need arise.
- b. CBOC staff will be available by telephone for the remote telemedicine study provider should they need to emergently contact an on-site VA staff.
- c. If a patient becomes suicidal, homicidal, psychotic, or agitated, the Telehealth provider will ask for assistance from the CBOC staff who would help in deescalating the patient and/or initiating commitment.

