For RCT phase, structured clinical interviews will take place at Baseline (week 0) and posttest (within 4 weeks of final session). Self reports/surveys will take place at Baseline (during week 0) and at posttreatment (during final session). For drop out Veteran participants, posttest surveys will be completed 16 weeks post-session 1 and the posttreatment clinical assessment will be done within 4 weeks of that posttest survey. For late treatment completers (i.e., treatment takes more than 16 weeks), all posttest surveys and post clinical interviews will be delayed but will be done no later than 24 weeks post-session 1.

For the IC phase, weekly surveys will be given for the first 2 weeks of treatment (session 2a, and 2b). For the RCT phase, weekly surveys will be given during weeks 2, 4, 5, 6, 8, 10 and 12 of treatment. For participants, the weekly surveys during week 2 and 8 will be lengthier and more thorough. All structured interviews (CAPS-5³ and SCID-5-CT)¹² will be administered by trained and supervised assessors who are blinded to condition. Assessors will be trained and supervised weekly by [name], a licensed clinical psychologist with expertise in conducting structured diagnostic clinical interviews and assessing and intervening with patients experiencing mental health crises. For mailed assessments, we will use CCDOR's well-established modified-Dillman protocol with repeated mailings and an incentive (incentive schedule described below).⁶ For surveys of Veterans with PTSD, our team's response rates

have ranged from 55% to 85%. Given the short interval between assessments, we will include a telephone call reminder and an offer telephone administration to optimize response rates.⁶

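### Do the six-week dropout rule and the week-16 survey leave no posttreatment PCL-5 date for Veterans who go silent late in treatment?

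*Combined protocol and SAP*

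**What the plan says.** - Section 5.1F deals with the case where "Participants could, without notice, stop coming to treatment". It provides that "any unanticipated break in treatment for longer than 6 consecutive weeks will trigger an official 'end' to their treatment period", keeps these Veterans in all study assessments, and adds: "They will be assessed at 16 weeks post session 1 for their posttreatment survey and interview".
- Section 5.5A.2 gives the same survey date ("For drop out Veteran participants, posttest surveys will be completed 16 weeks post-session 1") and places the clinical interview within four weeks of that survey. For those whose treatment runs past 16 weeks, "all posttest surveys and post clinical interviews will be delayed but will be done no later than 24 weeks post-session 1".
- Section 5.1C says: "If participants are still in treatment at 16 weeks post-session 1, the posttreatment assessment will be delayed". The stated reason is to let them get further through therapy first.
- The opening of Section 5.5A gives 16 weeks after session 1 as the Aim 2 posttreatment time point, without exceptions.
- Section 5.1D plans "11 total sessions delivered over an 11-16 week period".
- Section 5.1K.1, on reports of partner violence, says a therapist closes a case on completion of treatment, and also "when the veteran tells their therapist they have quit PE, or when providers have exhausted outreach attempts".

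Section 5.5A.4 names the PCL-5 as the main Aim 2 outcome. Section 5.6A names session attendance as the primary outcome.

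**The concern.** Read literally, three rules meet at week 16. A Veteran who stops attending without notice late in the course has not yet been away for more than six weeks. Under Section 5.1F alone that Veteran's treatment has not officially ended, so Section 5.1C seems to call for a delay. If the Veteran never returns, Sections 5.1F and 5.5A.2 then say the survey was due on a date already past. The right date would depend on attendance that has not yet happened.

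At stake would be the timing, or the loss, of the PCL-5 score in Veterans with interrupted attendance, which hypothesis H1a expects to differ by arm. Providers deliver both conditions and hold the attendance information, so the judgement that a silent Veteran is still in treatment could be made by someone who knows the assignment. The three-month follow-up is counted from the posttreatment assessment, so it would move too.

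**Working it through.** The plan states no figure to reproduce. The check is calendar arithmetic, a rough count, and a reading of the sections side by side.

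**Calendar.** Count weeks from session 1 and let L be the week of the last attended session. The break exceeds six weeks just after L + 6.

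| L | Break exceeded just after week | Weeks past week 16 |
|---|---|---|
| 9 | 15 | none |
| 10 | 16 | 0 |
| 12 | 18 | 2 |
| 14 | 20 | 4 |
| 16 | 22 | 6 |
| 18 | 24 | 8 |

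The overlap begins at L = 10. Beyond L = 18 the break is exceeded only after week 24, a limit written for late completers.

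**How many Veterans.** Section 2.0 gives dropout of about 35%, and 0.35 × 156 = 54.6. Assume 11 evenly spaced sessions with the last at week F, so session k falls at (F/10)(k − 1). The sessions k ≤ 10 that fall past week 10 are:

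- F = 10 or 11: none.
- F = 12: session 10.
- F = 13 or 14: sessions 9 and 10.
- F = 15 or 16: sessions 8, 9 and 10.

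If stopping is equally likely after each of sessions 1 to 10, the share of dropouts affected runs from 0 to 30%, or 0 to 0.30 × 54.6 = 16.4 Veterans. With F spread uniformly over weeks 10 to 15 or 10 to 16, the average share is 14.2% or 16.8%, which is 7.8 or 9.2 Veterans. If stopping is front-loaded (weights 10 down to 1), it is 4.0% or 5.2%, which is 2.2 or 2.8 Veterans, and at most 6/55 = 10.9%, or 6.0. The spacing, the stopping pattern and the spread of F are all assumptions. Veterans who announce that they are quitting lower the count; those who pause and return raise it.

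**What that could do.** Section 5.6A2 allows for 156 − 124 = 32 missing posttreatment scores. If every affected survey were lost, 2 to 9 would use 2/32 = 6% to 9/32 = 28% of that allowance, and 16 would use half. Late classification is not loss, however. If instead all 9 were in one arm of 78 and each was surveyed six weeks late (L = 16, the top of the planned course), that arm's mean survey date would move by 9 × 6/78 = 0.7 weeks; for 16 Veterans it would be 16 × 6/78 = 1.2 weeks. Both are deliberately extreme. The documents give no rate of PCL-5 change per week with which to turn them into points.

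**The sections side by side.**

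1. Section 5.1C delays for a purpose: further progress through therapy. Section 5.5A.2 delays for people who complete late. A Veteran who has gone silent is not evidently either.
2. Section 5.1F says a long break ends treatment. It does not say that nothing else does. Section 5.1K.1 shows that therapists also close cases on notice of quitting or after failed outreach.
3. Section 5.5A supplies week 16 as the general date, and Sections 5.1F and 5.5A.2 repeat it for dropouts.

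Week 16 as the default, with delay for those actively attending, is consistent with all of these and needs no knowledge of later attendance.

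**The case for a change.** The best case for a change is that no section states this default. The closing rule in Section 5.1K.1 serves the review of partner-violence reports, carries no time limit and is not tied to assessment dates. The 24-week limit is not written for dropouts, and extending it would bound the date without fixing it. Only the interview assessors are stated to be blinded. All of that stands: the reader has to infer the rule.

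What does not stand is that the outcome is thereby put at risk. The documents nowhere give treating providers the decision on survey dates. The PCL-5 is self-reported. Section 5.5A.3 provides repeat mailings, a postcard, calls and telephone administration, so a return in the exact week was never to be expected. Section 5.5A.4 also has the PCL-5 collected during treatment. Six of the seven scheduled treatment surveys (weeks 2, 4, 5, 6, 8 and 10, but not 12) fall by week 10, although the documents do not say which of them carry the scale. Section 5.6B2 models scores over time and plans both available-data and imputed analyses.

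The obvious remedy is to survey everyone unfinished at week 16 and again at the end of treatment, but it offers no clear gain. It surveys people whose assessment Sections 5.1C and 5.5A.2 say is to be delayed. Choosing between the two scores by later attendance keeps the dependence it was meant to remove. It also leaves open which survey starts the three-month clock and when support persons respond. If 10% to 25% of the 156 were unfinished (an assumption), it would mean 16 to 39 extra surveys, or 800 to 1,950 dollars at the 50-dollar incentive, plus an amendment.

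The smaller discrepancies are clerical or harmless. Section 5.1C omits the word weeks for Veterans who never start. Section 5.5A gives the general date without its exceptions. The interview is put at week 16 in Section 5.1F and within four weeks of the survey in Section 5.5A.2.

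**Conclusion.** The calendar observation is correct: for Veterans last seen at week 10 or later who go silent, the text does not say explicitly which rule governs on the day week 16 arrives. It does not follow that the date cannot be determined. This is an unwritten operational detail that staff can fill sensibly from the general time point and the stated purpose of the delay.

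The group is small: about 2 to 9 Veterans on average and 0 to 16 across the assumptions, all resting on a 35% literature dropout rate, even session spacing and assumed stopping patterns. Neither the size nor the direction of any effect on the PCL-5 contrast is shown, and session attendance is unaffected. Tabulating the actual assessment week by arm, which is ordinary reporting, would let a reader see whether timing differed. No change to the plan is called for.

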2.2 Strategies for Family Supported PE

2.2A. Structure of Standard PE.

The PE treatment protocol includes education, imaginal exposure (repeatedly imagining and describing a trauma memory to the provider), in vivo exposure homework (exposure to trauma reminders in real life), and listening to audio recordings of Veterans' trauma accounts between sessions (imaginal exposure homework).⁵² The first sessions are largely educational. Imaginal exposure begins in Session 3. Due to the volume of material provided in Session 2, in VA care, it is frequently divided into two sessions: 2a (education on PTSD and avoidance; detailed rationale for in vivo exposure) and 2b (building a hierarchy of situations to approach at home; see Figure 2).

2.2B. Overview of Family Supported PE.

SPs will attend PE Sessions 1, 2a, and 2b; receive two check-in telephone calls; and be invited to elective in-person check-ins if indicated (see below). Dividing Session 2 into 2a and 2b allows for more time to discuss the content outlined below. Strategies for how to engage with families are drawn from existing evidence-based approaches. The goals for family engagement are to 1) educate SPs about how avoidance maintains PTSD, 2) facilitate discussion of how SPs encourage/discourage PE participation (accommodation), and 3) develop a plan, tailored to the Veteran-SP dyad, for how SPs will help Veterans participate (support plans). The VHA Blueprint for Excellence emphasizes patient-centered care,⁴⁰ which is both flexible and tailored.⁴⁴ Flexibility is essential to implementation of family involved treatments,⁷⁶ and to improving the clinical relevance of interventions.¹⁴ Consequently, inclusion/exclusion criteria only require Veterans bring a SP to Session 1 (if randomized), and discuss further SP attendance with their provider.

2.2C. Description of Strategies.

[figure not shown]

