IPV reports on surveys. Baseline, weekly, and posttreatment surveys ask about intimate partner violence (IPV). IPV reports are not routinely considered psychiatric emergencies that warrant breaching participants' confidentiality. Additionally, reaching out to all those who endorse IPV may have unintended negative consequences. Reaching out when uninvited to ask IPV victims to further discuss their IPV may be distressing and bring up traumatic memories. The outreach may be unwelcome, perceived as intrusive, and discourage future reporting. Discussing violence over the phone may also place the victim at risk to be overheard by the abuser, other loved ones, or children in the home. Consequently, a list of resources will be included with baseline, posttreatment, and follow-up surveys, including for IPV. Letters accompanying surveys will encourage respondents to contact study staff if they would like to discuss any of their survey responses. We will rely on participants to contact study staff if they wish to discuss their IPV experiences further. If participants are excluded due to IPV, the staff member notifying the reporter of their exclusion will offer local and national resources for IPV.

When the IPV reporter is actively engaged in psychotherapy in our study (i.e., veterans who are actively participating in PE and loved ones are actively participating in PE2), the reporter has an ongoing relationship with their study provider. In this circumstance, the reporter has the

reasonable expectation that the provider is reviewing their surveys and may ask them more about it. Thus, when a participant is actively engaged in psychotherapy in our study, providers will review IPV survey responses and intervene as clinically indicated, keeping the safety of the reporter of paramount concern. Providers will not breach the reporter's confidentiality unless they have the reporter's verbal permission or are concerned they must do so to prevent imminent harm.

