5.4 Informed Consent Procedures

5.4A. SP Informed Consent.

We will seek an approval of verbal informed consent over the phone and waiver of written informed consent. All contact between study staff and SPs randomized to standard PE (without family involvement) will be remote (i.e., by mail and telephone). The study poses minimal risks, waiving informed consent does not affect the well-being of participants, and decreases participant burden that would be associated with scheduling and attending an in-person appointment at the VA hospital, especially for SPs who have full time jobs and have never been to the VA hospital. Verbal consent will be obtained by telephone, pending final confirmation of Veteran's eligibility at the eligibility assessment/consent described above.

During the initial phone call with SPs, all study procedures (assessment data gathering, intervention, audiotaping) will be fully described to the participant using the Information Sheet SPs received by mail to guide the discussion. Participants will be informed of the study design (including, for RCT participants, that they will be randomized to condition and will receive notice of their condition after the Veteran signs informed consent documents and Veteran eligibility is finalized) before they decide to participate. After reviewing the study and answering all questions, for those SPs who remain interested in participating, the consenting staff will ask to audio record their consent to the study and consent to audio recording treatment sessions (if assigned to family supported PE).

If Veterans are deemed ineligible due to inclusion/exclusion criteria or lack of interest, SPs will be informed that full inclusion/exclusion criteria were not met for the Veteran and thus the dyad is no longer eligible for enrollment. Specific details on which inclusion/exclusion criteria (including level of interest in the study) will not be disclosed. The same approach will be used for SPs' who decline participation or report moderate relationship aggression (i.e., Veterans will be informed that full inclusion/exclusion criteria were not met and thus the dyad is no longer eligible for enrollment). Appropriate alternative referrals to mental health treatment, including substance use treatment or psychotherapy, or to address relationship aggression will be made as upon request and when clinically indicated (i.e., positive screens for psychosis, substance use, suicidality, homicidally, etc.).

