IC phase: Participants will receive a \$25 incentive for Baseline self-reports, \$40 optional for baseline Cognitive Interviews, \$50 for optional Baseline Structured Clinical Interviews (Veterans only), \$5 per Weekly form, \$25 for Posttreatment self-reports, \$40 for optional posttreatment Cognitive Interviews, and \$50 for optional Posttreatment Structured Clinical interviews (Veterans only). Veterans can earn up to \$250 and \$170 for SPs. Telephone administration will be offered for interviews to increase response rates.

RCT Phase: Participants will receive a \$40 incentive for Baseline self-reports, \$50 for Baseline interviews (Veterans only), \$50 for Posttreatment self-reports, \$60 for Posttreatment interviews (Veterans only), and \$60 for 3-month follow-up self-reports. Veterans and SPs will be given weekly surveys during weeks 2, 4, 5, 6, 8, 10 and 12 of treatment. Participants will be

compensated \$10 for completing surveys during weeks 4, 5, 6, 10 and 12. The weekly surveys during week 2 and 8 will be lengthier and more thorough, thus participants will be paid \$20 for completing weekly surveys on those two weeks of treatment. Veterans can earn up to \$290 and SPs' \$190. Telephone administration will be offered for to increase response rates.

Up to 40 Veterans randomized to Partner Enhanced PE will be offered the opportunity to complete an over-the-phone qualitative interview. Veterans who are offered and complete the qualitative interview will be compensated \$60. The incentive for the qualitative interviews will not be reflected in the total amount a Veteran can receive, because it will not be offered to all participants.

5.4F. Communicating with Participants using MyHealtheVet Secure Messaging.

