5.5A.3 Exploratory Aim. Exploratory Aim outcomes (key social influences) will be measured from self-reports from both Veterans and SPs at Baseline, Posttreatment, and Weekly intervals. The frequency of measurement is necessary for examining the nature, shape, and change of key social influences week-by-week over the course of treatment. For the IC phase, the Weekly self-report for Veterans will be completed before each treatment session with a \$5 incentive for each form. IC phase participants will only receive these assessments for the first 3 weeks of treatment (session 2a and 2b). For the RCT phase, Veterans and SPs will be given surveys during weeks 2, 4, 5, 6, 8, 10 and 12 of treatment. Participants will be compensated \$10 for completing each survey during weeks 4, 5, 6, 10 and 12. The weekly surveys during week 2 and 8 will be lengthier and more thorough, thus participants will be paid \$20 for completing weekly surveys on those two weeks of treatment. Staff will make reminder calls to Veterans to ensure these weekly surveys are completed and offer telephone administration. SP data collection will take place by mail or online, because if SPs in standard PE receive assessments with Veterans at the medical center, we may unintentionally increase the rates of SPs reaching out to providers, artificially inflating family assistance within standard PE (i.e., cross-over effects). Veteran and SP participants are required to complete their baseline assessment survey before beginning treatment, as the baseline survey is part of study eligibility criteria. Participants will be given a \$40 incentive for the baseline surveys. Veteran and SP participant posttreatment assessments will be administered using CCDOR's modified-Dillman protocol, with a \$50 incentive for Posttest surveys, as well as a post-card reminder, second and third survey mailing package, telephone call reminders, and an offer of telephone administration to optimize response rates.⁶ For Weekly assessments, SPs from both conditions will receive a packet of self-report forms and postage paid envelopes at study enrollment (RCT only, these measures will be administered in person when SPs attend sessions in the IC phase). SPs will mail completed self-report forms to staff weekly and receive their incentive for each completed form. Study staff will make reminder calls each week to participants to complete the weekly survey. If study staff fail to reach a participant, another weekly survey will be sent along with a letter reminding him/her to complete the survey and mail back to the VA. For the few sessions that SPs in family supported PE attend, they will be offered in person administration of their weekly forms for convenience. We will also send Veterans and SPs a follow-up survey 3 months after the posttreatment assessment. Participants will receive a \$60 incentive for completing the 3 month follow-up survey, and we will use CCDOR's modified-Dillman protocol once again to optimize response rates. See attached Materials for study measures.

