5.6B4. Exploratory Aim. For this Aim, we will test if differences between family supported PE and standard PE are mediated by the key social influences targeted by family supported PE (e.g., treatment condition → family support for PE participation → session attendance). Mediators include weekly scores on the CEQ-PTSD⁹⁶ (SP report), SORTS⁹⁷ (SP report), and Support Checklist (Veteran report). Analytic approaches will be similar to Aim 1, with social influence variables incorporated as mediators. This basic mediation model is a special case of random effects structural modelling, where each equation will have random intercept and provider terms, adjusted for site fixed effects. Indirect effects for mediators treated as single summary scores will be directly tested using bootstrapped confidence intervals¹⁰⁵ to avoid the often-violated assumption underlying Sobel's (1982) method that the sampling distribution of the indirect effect is normal. Analyses will also examine differences between conditions on the rate and shape of change in key social influences.

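### Weekly support-person forms may be completed in person in the family arm only, so completion setting is tied to arm for two exploratory mediators, mainly at week 2

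*Combined protocol and SAP*

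**What the plan says.** Section 5.5A.3 sets remote collection for SPs and gives a reason: "SP data collection will take place by mail or online, because if SPs in standard PE receive assessments with Veterans at the medical center", they might be prompted to approach providers. Section 5.4A agrees: "All contact between study staff and SPs randomized to standard PE (without family involvement) will be remote (i.e., by mail and telephone"). The starting point is the same in both arms: "SPs from both conditions will receive a packet of self-report forms and postage paid envelopes at study enrollment". Reminder calls and re-mailing of weekly forms are not limited to one arm. Under RCT incentives, 5.4E adds "Telephone administration will be offered for to increase response rates", also without limiting it to one arm.

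Section 5.5A.3 then departs from this for one arm: "For the few sessions that SPs in family supported PE attend, they will be offered in person administration of their weekly forms for convenience". Section 2.2B names the sessions: "SPs will attend PE Sessions 1, 2a, and 2b; receive two check-in telephone calls". It also allows elective in-person check-ins.

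On the analysis side, 5.6B4 states: "Mediators include weekly scores on the CEQ-PTSD". It lists SORTS as a second SP-reported mediator and the Support Checklist as a Veteran-reported one. It also plans to compare the arms on how quickly, and in what pattern, these scores change. The model terms are a random intercept, a provider term and site. The document does not describe recording where or how a form was completed, adjusting for it, or repeating an analysis without in-person forms.

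**The concern.** CEQ-PTSD and SORTS ask SPs how credible the treatment seems and how far they accommodate symptoms. Both are subjects of the sessions that family-arm SPs attend. An answer given in the clinic may differ from one given at home, whether through social desirability or prompting by the surroundings. If that happens in one arm only, part of any arm difference on these scores reflects setting rather than a change in the SP.

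Two planned results are exposed: the treatment-to-mediator path, and the comparison of mediator trajectories. The early readings matter most for the second. Week 2 is the first weekly form, and it is one of the two longer ones.

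**Working it through.** The plan gives no power or error figure for the Exploratory Aim, so there is none to reproduce. The sample size of 78 per arm comes from 5.1. It is consistent with the plan's primary power statement: a two-session difference with SD 4.45 gives 80.1% power, against the stated 80%.

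**Which forms are exposed.** Forms fall in weeks 2, 4, 5, 6, 8, 10 and 12 (5.5A.3). Treatment is 11 sessions over 11 to 16 weeks (5.1D). Assume even spacing over a span of S weeks, so the gap is (S − 1)/10.
- S = 11 to 15: Sessions 1, 2a and 2b fall in weeks 1, 2 and 3. Only the week 2 form coincides with an attended session.
- S = 16: they fall in weeks 1, 2 and 4. The week 2 and week 4 forms coincide.

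So about 1 of 7 forms is exposed, or 2 of 7 at the slowest pace, before any elective check-ins.

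**Assumptions for the size.** There is no true arm effect. Every family-arm SP uses the option. In-person completion shifts the score by b SD, with b = 0.2 to 0.4. All 78 SPs per arm return all forms. Correlation between any two forms is 0.61, borrowed from the PCL value in 5.6A2 because the plan gives none for the SP scales. The test is two-sided at 5%, with noncentrality d × √(78/2) = 6.245d and a noncentral t with 154 df.

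**(a) Week 2 form alone.** d = b.
- b = 0.2: noncentrality 1.249, rejection rate 23.7%.
- b = 0.4: noncentrality 2.498, rejection rate 69.9%.

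**(b) Linear slope over the seven forms, week 2 exposed.** Mean week = 47/7 = 6.714. Sum of squares = 389 − 47²/7 = 73.43. The slope shifts by b × (6.714 − 2)/73.43 = 0.0642b. The SD of a person's slope is √((1 − 0.61)/73.43) = 0.0729. So d = 0.881b.
- b = 0.2: d = 0.176, rate 19.4%.
- b = 0.4: d = 0.352, rate 59.0%.

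**(c) Mean of the seven forms.** The SD of the mean is √((1 + 6 × 0.61)/7) = 0.816. With one form exposed, d = (b/7)/0.816 = 0.175b; with two, d = 0.350b.
- One form: 5.5% at b = 0.2 and 7.2% at b = 0.4.
- Two forms: 7.2% and 14.0%.

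**Partial uptake.** If half the family-arm SPs use the option, the average shift halves. The range b = 0.2 to 0.4 then acts roughly like 0.1 to 0.2, and the rates become about 9.5% to 23.7% for (a) and 8.5% to 19.4% for (b).

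With the same mode in both arms the setting shift is zero and the rate returns to 5%.

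**The case against.** The strongest reply is that little is exposed. In-person completion is optional and touches one or two of seven forms. No stand-alone week 2 test is planned, and an average over all forms barely moves. Willingness to use telehealth (Table 4) and online surveys as the main mode (5.5A.7) reduce how often the option can arise. All of this stands, and it makes the point minor. It does not remove the asymmetry, and the planned comparison of change over time leans on the early readings.

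A reader might draw stronger conclusions that the documents do not support:
- **That the trial would report a false mechanism at these rates.** The indirect effect also needs a path from mediator to attendance. The rates above concern only the treatment-to-mediator path and the trajectory comparison.
- **That family-arm SPs answer straight after being taught about accommodation.** For RCT forms, 5.5A.3 does not say whether completion precedes or follows the session. In the coaching phase, 5.5A.2 places the forms before Sessions 2a and 2b.
- **That missing forms depend on SP attendance in one arm.** An SP who does not attend still has the packet, the reminders and the re-mailing. In-person completion is an additional route.
- **That an expected provider audience is part of the setting effect.** Section 5.1K.1 does mention a "reasonable expectation that the provider is reviewing their surveys and may ask them more about it", but under reports of partner violence. It turns on active engagement in therapy and applies wherever the form is completed. Identical wording in both arms about who sees the answers would conflict with that section.
- **That standard-PE SPs are confined to mail or online.** Telephone also appears to be available to them.

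It is also fair to say that SPs know their arm, so expectation-driven reporting would remain with home completion. Removing the option takes away only the added effect of setting.

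**Conclusion.** The point holds as a minor one. By design, completion setting differs by arm for the two SP-reported mediators, and the plan neither records nor handles it. The direction and size of a setting effect cannot be found in the documents; 0.2 to 0.4 SD is an assumption. Under that assumption and full uptake, the distortion is material for an early-form or slope comparison and small for an average over all weekly forms. The slope figure also depends on the assumed equal correlation and on a straight-line model with only week 2 exposed.

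The session-attendance primary outcome, the PCL-5 and the Veteran-reported Support Checklist are unaffected.

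**What to change.** In 5.5A.3, delete the in-person option for SPs in the RCT phase, so that both arms use the same remote modes (mail, online or telephone) with the existing packet, reminder calls and re-mailing. Record the completion mode of every SP weekly form. In 5.6B4, state that the mediator and trajectory analyses will be repeated without any forms already completed in person.

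The cost is a short amendment and one extra data field. Family-arm SPs lose a little convenience, and a few early forms may not come back. The follow-up procedures already in place should limit that loss.
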